## 3 OBJECTIVES AND PURPOSE

### 3.1 PRIMARY OBJECTIVE

To determine efficacy of pomalidomide compared to placebo for the reduction in severity of epistaxis after 24 weeks of treatment.

### 3.2 SECONDARY OBJECTIVES

1. To determine the safety and tolerability of pomalidomide for the treatment of HHT.
2. To determine if pomalidomide treatment improves quality of life in HHT.
3. To determine whether a continued response to pomalidomide is evident 4 weeks after treatment discontinuation.
4. To develop a biorepository for future studies to define biomarkers predictive of pomalidomide response and allow investigations into the biology of HHT and mechanisms of pomalidomide.

## 4 STUDY DESIGN AND ENDPOINTS

### 4.1 DESCRIPTION OF THE STUDY DESIGN

This is a multi-center, double blind, placebo-controlled study that will investigate the efficacy and safety of pomalidomide in patients with HHT and chronic epistaxis leading to iron-deficiency anemia or requiring intravenous iron infusions or blood transfusion.

After recruitment, patients will be screened for study eligibility. The screening evaluation will include the ESS with three month recall, which will reflect the patient's history of epistaxis and bleeding over the prior three months, as well as detailed review of iron infusion and red cell transfusion over the preceding six months. Eligible patients will be provided a diary to record the duration of each epistaxis event that occurs during the 4 weeks prior to the baseline visit. Eligible patients will then return for the baseline randomization visit between 28 and 56 days later, at which time patients will undergo genetic testing, if this has not been previously performed or if results for ENG, ACVRL1 and SMAD4 genes are not available. A repeat ESS with 4 week recall will be performed and will be considered the "baseline" ESS. Patients will also complete QOL surveys at this visit. Patients will then be randomized 2:1, stratified by study site, to either pomalidomide, 4 mg/day for 28 days during each of six 28 day cycles (24 weeks), or placebo, administered on an identical schedule.

Patients will be seen every four weeks during the study to measure the ESS (with 4 week recall), measure iron stores, and obtain laboratory studies, which will include CBC, metabolic profile and iron studies. The iron replete state will be defined as a ferritin  $\geq$  50 ng/ml and a transferrin saturation  $\geq$  30% (since ferritin levels may be elevated due to concurrent inflammation). Investigators will be encouraged to replete iron stores in patients in both arms of the study based on these parameters, and the amount of iron infused (in mg) recorded. There is no mandate for the use of a particular iron preparation. Investigators will be encouraged to use iron infusions prior to blood transfusion, though the latter will be mandated for a hemoglobin below 6.5 gm/dl, and recorded as units of packed red blood cells administered. Blood transfusion may also be given at the investigator's discretion based on symptoms that may include shortness of breath, severe fatigue, or other cardiovascular manifestations. Patients will be assessed for adverse events (AE) throughout the study. Treatment dosage may be reduced, or temporarily or permanently discontinued following AE-specific guidelines related to fatigue, cytopenias or other toxicities.

The effect of pomalidomide on QOL will be assessed by measuring QOL at the baseline visit, at the 12 and 24 week visits, and at the 4 week post-treatment follow-up visit using validated NIH instruments of 1) Neuro-QOL satisfaction with social roles and activities, 2) PROMIS emotional distress – depression, and 3) PROMIS fatigue. We will also assess responses to an HHT specific questionnaire developed specifically for this study and shown to correlate with these PROMIS items. The effect of pomalidomide on duration of epistaxis will be assessed via diary between weeks 8-12, 20-24 and the 4 weeks post-treatment discontinuation.

---

#### 4.2.1 PRIMARY ENDPOINT

The primary endpoint of this study is change of the Epistaxis Severity Score from baseline to week 24 in the placebo and pomalidomide-treated groups. The ESS at baseline and each follow-up visit will reflect the patient's symptoms and bleeding over the previous 4 weeks.

---

#### 4.2.2 SECONDARY ENDPOINTS

##### **Key Secondary endpoints**

1. Amount of parenteral iron administered (in mg) during the 24 week treatment period in the pomalidomide and placebo groups (calculated as average mg/4-week interval to account for patients who discontinue early).
2. Amount of packed red blood cell transfusions (in units) during the 24 week treatment period in the pomalidomide and placebo groups (calculated as average units/4-week interval to account for patients who discontinue early).
3. Change in Neuro-QOL™ Satisfaction with Social Roles and Activities Short Form (V1.1) T-score from baseline (randomization visit) to weeks 12 and 24 (key timepoint), and the 4 week post-treatment follow-up visit in the pomalidomide and placebo groups. Although developed as part of an assessment system for people with neurological conditions, the Satisfaction with

Social Roles and Activities is scored relative to a general population sample, supporting its use in non-neurologic health conditions.

4. Change in the HHT-specific QOL total score from baseline to weeks 12 and 24 (key timepoint), and the 4 week post-treatment follow-up visit in the pomalidomide and placebo groups.
5. Change in average weekly epistaxis duration from the four week screening period prior to baseline to weeks 8-12 and to weeks 20-24 (key timepoint), and to the 4 weeks post-treatment in the pomalidomide and placebo groups.

#### **Other Secondary endpoints**

6. Change in PROMIS® Emotional Distress – Depression Short Form (V1.0) T-score from baseline (randomization visit) to weeks 12 and 24 (key timepoint), and the 4 week post-treatment follow-up visit in the pomalidomide and placebo groups.
7. Change in PROMIS® Fatigue Short Form (V1.0) T-score from baseline (randomization visit) to weeks 12 and 24 (key timepoint), and the 4 week post-treatment follow-up visit in the pomalidomide and placebo groups.
8. Proportion of patients requiring no red blood cell transfusion or parenteral iron infusion during the 24 week treatment period in the pomalidomide and placebo groups.
9. Change in the ESS from baseline to that recorded at each individual patient assessment, including the 4 week post-treatment follow-up visit.
10. Change in the ESS from baseline to the average of the week 16, 20 and 24 assessments.
11. Proportion of patients requiring endoscopic interventions for management of bleeding during the 24 week treatment period in the pomalidomide and placebo groups.
12. Incidence and severity of adverse events in the pomalidomide and placebo groups including but not limited to:
  - Venous thromboembolism
  - Arterial thromboembolism
  - Thrombocytopenia
  - Neutropenia
  - Peripheral neuropathy
  - Fatigue
  - Constipation/diarrhea
  - Rash
  - Any other AEs or SAEs of at least moderate severity that are possibly related to pomalidomide
13. Change in iron/hemoglobin-related studies including iron saturation, ferritin, hemoglobin, hematocrit, MCV, and MCHC.

---

#### **4.2.3 EXPLORATORY ENDPOINTS**

1. Rate of relapse at the 4 week post-treatment follow-up visit, where relapse is defined as a return of the ESS to the baseline value or greater in pomalidomide (or placebo)-treated subjects.
2. Median time after initiation of pomalidomide to obtain a decrease in the ESS of at least 1.0 in the in pomalidomide-treated subjects compared to placebo.
3. Effect of genotype on the response to pomalidomide.

## 5 STUDY ENROLLMENT AND WITHDRAWAL

### 5.1 PARTICIPANT INCLUSION CRITERIA

1. A clinical diagnosis of HHT as defined by the Curacao criteria
2. Age  $\geq$  18 years
3. Platelet count  $\geq 100 \times 10^9/L$
4. WBC  $\geq 2.5 \times 10^9/L$
5. INR  $\leq 1.4$  and normal  $\pm 2$  sec activated partial thromboplastin time (aPTT or PTT per local laboratory designation) by local laboratory criteria (except for patients on a stable dose of warfarin or direct oral anticoagulants)
6. Epistaxis severity score  $\geq 3$  measured over the preceding three months, measured at the screening visit
7. A requirement for anemia, as determined by local laboratory hemoglobin assessment and normal ranges, and/or parenteral infusion of at least 250 mg of iron or transfusion of 1 unit of blood over the 24 weeks preceding the screening visit
8. All study participants must agree to be registered into the FDA mandated POMALYST REMS® program, and be willing and able to comply with the requirements of the POMALYST REMS® program
9. Females of childbearing potential (FCBP)† must adhere to the pregnancy testing schedule mandated by the POMALYST REMS® program (see Section 8.4.5)
10. Ability to understand and sign informed consent

†A female of childbearing potential is a sexually mature woman who: 1) has not undergone a hysterectomy or bilateral oophorectomy; or 2) has not been naturally postmenopausal for at least 24 consecutive months (i.e., has had menses at any time in the preceding 24 consecutive months).

### 5.2 PARTICIPANT EXCLUSION CRITERIA

1. Women currently breast feeding or pregnant
2. Renal insufficiency, serum creatinine  $> 2.0 \text{ mg/dl}$
3. Hepatic insufficiency, bilirubin  $> 2.0$  (or  $> 4.0$  in the setting of a prior clinical or genetic diagnosis of Gilbert's syndrome) or transaminases  $> 3.0 \times \text{normal}$
4. Prior treatment with thalidomide or other Immunomodulatory imide drugs (IMiDs) within previous 6 months
5. Prior treatment with bevacizumab (systemic or nasal) within previous 6 weeks\*

6. Prior treatment with pazopanib within previous 6 weeks\*
7. The use of octreotide or oral estrogens within the previous month\*
8. History of prior unprovoked thromboembolism confirmed by venous ultrasound or other imaging modalities
9. Known peripheral neuropathy, confirmed by neurologic consultation
10. Known underlying hypoproliferative anemia (i.e. myelodysplasia, aplastic anemia)
11. Currently enrolled in other interventional trials
12. Known hypersensitivity to thalidomide or lenalidomide
13. The development of erythema nodosum if characterized by a desquamating rash while taking thalidomide or similar drugs
14. Known *SMAD-4* mutation, unless there has been a colonoscopy with normal (negative) results, or in which the patient has had no more than 5 small (in the opinion of the gastroenterologist) colonic polyps completely removed within the preceding 18 months
15. Anything that in the investigator's opinion is likely to interfere with completion of the study

\* Use of these treatments is not permitted during study participation. See protocol section 7.6 for additional details regarding prohibited treatments.

### 5.3 STRATEGIES FOR RECRUITMENT AND RETENTION

We estimate that we will need to screen 200 patients in order to enroll and randomize 159 participants (106 treated with pomalidomide, 53 with placebo), assuming 80% of screened patients will enroll.

To meet this recruitment goal, patients will be recruited at each of up to 15 institutions all of which are nationally-designated HHT Centers of Excellence; three of these centers contributed patients to the NOSE study, with our Utah site being the highest enroller. A national recruitment process will also be employed through the outreach of CureHHT, an international patient advocacy group that communicates regularly with more than 10,000 HHT patients. Details describing the trial will be posted on the CureHHT website and the study website maintained by the DCC after approval from the central IRB at the Cleveland Clinic. CureHHT will publicize the trial through regular email blasts to its constituency and mailings. The trial will also be listed on [www.clinicaltrials.gov](http://www.clinicaltrials.gov).

Randomization will be performed in a 2:1 manner to enhance patient enthusiasm for participation in the trial. To alleviate the risk of exposure to COVID-19, site PIs will be given the flexibility to conduct some of the research visits remotely. We anticipate that half of the patients will be recruited from existing populations treated at the study sites, and that half of the patients will respond to communications issued through CureHHT and other mechanisms. Original study timelines were that enrollment would be completed within 2.5 years, with each site screening 9 to 10 patients and randomizing 6-8 patients per year. However, the COVID-19 pandemic has impacted enrollment prolonging study timelines.

### 5.4 PARTICIPANT WITHDRAWAL OR TERMINATION

#### 5.4.1 WITHDRAWAL OR TERMINATION OF SUBJECTS FROM THE STUDY

Subjects will be encouraged to remain in the study until completion, but informed that they have the right to stop taking medication or withdraw from the study at any time without compromise to their subsequent care. Causes for study withdrawal may include unacceptable side-effects, a decision to pursue another treatment modality, or personal issues that preclude continued study participation. If a subject elects to stop taking study medication or if study medication is permanently stopped by the study PI due to toxicity concerns, they should be encouraged to complete follow-up visits after stopping study medication as indicated in Section 7.3.5.

#### 5.4.2 HANDLING OF PARTICIPANT WITHDRAWALS OR TERMINATION

For subjects who withdraw from the study, data collected up to the time of study withdrawal will remain in the trial database and will be used in the analysis. A discussion of how data from subjects with early treatment stop or early study withdrawal will be handled in the statistical analysis is described in Section 10, Statistical Considerations.

### 5.5 PREMATURE TERMINATION OR SUSPENSION OF STUDY

This study may be temporarily suspended or prematurely terminated if there is sufficient reasonable cause. Written notification, documenting the reason for study suspension or termination, will be provided by the clinical coordinating center to NHLBI and the FDA. If the study is prematurely terminated or suspended, the PI will promptly inform the IRB and will provide the reason(s) for the termination or suspension. In the case of unanticipated, unacceptable risks to participants, the Principal Investigator will make the determination to terminate or suspend the study based on recommendations of the Medical Monitor or Data Safety Monitoring Board (DSMB).

Circumstances that may warrant termination or suspension include, but are not limited to:

- Determination of unexpected, significant, or unacceptable risk to participants
- Demonstration of efficacy that would warrant stopping (per DSMB review of interim analysis)
- Insufficient compliance to protocol requirements
- Data that are not sufficiently complete and/or evaluable
- Determination of futility (per DSMB review of interim analysis)

If suspended, the study may resume once concerns about safety, protocol compliance, and/or data quality are addressed and satisfy the sponsor, DSMB, IRB and/or FDA.

## 6 STUDY AGENT

### 6.1 STUDY AGENT(S) AND CONTROL DESCRIPTION

#### 6.1.1 ACQUISITION

Pomalidomide (POMALYST®) or placebo will be provided to research subjects for the duration of their participation in this trial at no charge to them or their insurance providers. Pomalidomide will be provided in accordance with the Celgene Corporation's POMALYST REMS™ program. Per the standard POMALYST REMS™ program requirements, all physicians who prescribe pomalidomide for research subjects enrolled into this trial, and all research subjects enrolled into this trial, must be registered in and must comply with all requirements of the POMALYST REMS™ program.

Drug will be shipped on a per patient basis by a contract pharmacy to the clinic site or research subject. In accordance with the POMALYST REMS™ program, only enough pomalidomide for one cycle of therapy (i.e., 28 days) will be supplied to the subject.

---

#### 6.1.2 FORMULATION, APPEARANCE, PACKAGING AND LABELING

Pomalidomide or matching placebo will be supplied as 4.0 mg capsules for oral administration. Capsules of 3.0 and 2.0 mg pomalidomide or matching placebo will also be provided for patients who experience hematologic toxicity, fatigue or muscle cramping thought to be drug related, per guidelines described in Section 6.1.8. The new dose may be initiated after the unused capsules from the previous dose are collected.

Pomalidomide is dispensed to research subjects as individual bottles containing capsules. Each bottle will identify the contents as study medication. It is suggested as a component of the pomalidomide REMS program that patients not open or extensively handle pomalidomide capsules. All bottles will contain the following warning label: "WARNING: POTENTIAL FOR HUMAN BIRTH DEFECTS."

Placebo will contain Microcrystalline Cellulose (Type PH-102) (Compendia: NF, Ph Eur, JP) and the Swedish Orange (6180) Opaque Global Capsule Shell (Coni-Snap). Placebo will be indistinguishable from pomalidomide.

---

#### 6.1.3 PRODUCT STORAGE AND STABILITY

The study drug and placebo should be stored at room temperature away from direct sunlight and protected from excessive heat and cold.

---

#### 6.1.4 PREPARATION

No preparation of pomalidomide is necessary.

---

#### 6.1.5 DOSING AND ADMINISTRATION

Females of child bearing potential must have two negative pregnancy tests to enter this trial, the first test being 10-14 days before and the second test within 24 hours prior to prescribing study drug. The dose of pomalidomide is 4 mg per day for days 1-28 of a 28 day cycle. For the purposes of this study, one cycle will be defined as 28 days. Subsequent cycles may begin within 5 days of completion of the

previous cycle, to allow time for patient assessment and provision of new drug to the study participant.

---

#### 6.1.6 ROUTE OF ADMINISTRATION

Pomalidomide capsules should be swallowed whole, and should not be broken, chewed or opened. Pomalidomide should be taken without food, at least 2 hours before or 2 hours after a meal (water is allowed), preferably around the same time each day.

---

#### 6.1.7 DOSING SCHEDULE

This study employs a fixed dose of 4 mg of pomalidomide daily. This is the FDA approved dose for multiple myeloma, and has been shown to be active in a pilot trial of pomalidomide for patients with HHT. In the event that patient experiences adverse events that cannot be managed, the dose may be reduced stepwise to 3 mg or 2 mg/day at the site PI's discretion.

---

#### 6.1.8 DOSE ADJUSTMENTS/MODIFICATIONS/DELAYS

Study drug dose may be reduced, or temporarily or permanently discontinued following the guidelines specified in the sections below.

---

##### 6.1.8.1 MISSED DOSE

If a dose of pomalidomide is missed, it should be taken as soon as possible on the same day, within 6 hours. If it is missed for the entire day, it should not be made up the next day. The regular dose should be taken on the next day. Vomitted doses should be considered as dose missed for the entire day.

---

##### 6.1.8.2 OVERDOSE

Patients who take more than the prescribed dose of pomalidomide should be instructed to contact study staff immediately to review the dose taken and symptoms, and determine if urgent medical care is necessary.

---

##### 6.1.8.3 DOSE ADJUSTMENT FOR HEMATOLOGIC TOXICITY

The primary toxicity of pomalidomide is hematologic. Hematologic toxicity will be monitored monthly during the study. Dose adjustments will be undertaken any time the hematologic parameters dictate, as described in the tables below. Table 1A lists the NCI CTCAE grading of adverse event severity related to neutropenia and thrombocytopenia. Table 1B lists the interventions that will be used for neutropenia or thrombocytopenia according to NCI CTCAE grade. There is a lower threshold for intervention and/or discontinuation of pomalidomide for either neutropenia or thrombocytopenia than in multiple myeloma, as HHT is not a malignant disease.

**TABLE 1A: NCI CTCAE FOR NEUTROPENIA AND THROMBOCYTOPENIA‡**

Adverse Event	Grade				
	1	2	3	4	5
Neutrophils (ANC)	<LLN- $1.5 \times 10^9/L$	<1.5- $1.0 \times 10^9/L$	<1.0- $0.5 \times 10^9/L$	< $0.5 \times 10^9/L$	Death
Platelets	<LLN- $75 \times 10^9/L$	< $75-50 \times 10^9/L$	< $50-25 \times 10^9/L$	< $25 \times 10^9/L$	Death

‡ Units for blood cells counts are expressed as  $10^9/L$ , which is equivalent to  $10^3/\mu\text{l}$  or  $10^3/\text{mcl}$ . ANC = absolute neutrophil count.

**TABLE 1B: INTERVENTIONS FOR NEUTROPENIA AND THROMBOCYTOPENIA BY NCI CTCAE GRADE**

Adverse Event	Grade				
	1	2	3	4	5
Neutrophils (ANC)	None	None	Interrupt pomalidomide treatment, follow CBC weekly Resume pomalidomide when ANC is $>1.0 \times 10^9/L$ , at 1 mg/day less than previous dose*	Interrupt pomalidomide treatment, proceed as for Grade 3	Off study
Platelets (thrombocytopenia)	None	None	Interrupt pomalidomide treatment, follow CBC weekly Resume pomalidomide when platelets are $>0.5 \times 10^9/L$ , at 1 mg/day less than previous dose	Off study drug permanently	Off study

\* For Grade 3 neutropenias in which the ANC is  $>0.8 \times 10^9/L$ , patient may remain on the same dose of drug for up to 1 week at which time a repeat CBC should be obtained. If the ANC is persistently less than  $1.0 \times 10^9/L$ , study drug should be discontinued until recovery of the ANC to  $>1.5 \times 10^9/L$  and the patient then restarted on the next lower dose.

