#### 6.1.8.4 DOSE DISCONTINUATION BASED ON INVESTIGATOR'S DISCRETION

Pomalidomide may be held for an indefinite period at the discretion of the investigator for reasons including but not limited to safety and/or patient benefit (for example, surgery or other drug or disease related or unrelated medical problem). Study drug can be resumed at the discretion of the investigator based on the investigator's opinion that it is safe to do so. Patients should still attend regular study visits while study drug is held.

If the study drug is held during a cycle, the patient may begin the next dose cycle even if the previous cycle was not completed, assuming that the reason for holding the drug was not due to an adverse event requiring dose adjustment.

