## 7.2 LABORATORY PROCEDURES/EVALUATIONS

### 7.2.1 CLINICAL LABORATORY EVALUATIONS

#### 7.2.1.1 STANDARD OF CARE LABORATORY STUDIES

##### **CBC**

A CBC with differential will be performed at the screening visit and at all other study visits. Hematologic toxicities of pomalidomide and their grading are discussed in Table 1A. The Hgb, WBC, absolute neutrophil count (ANC) and platelet counts at all study visits will be recorded.

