### 7.3.5 DISCONTINUATION OF STUDY MEDICATION

Study medication may be stopped by the study PI due to toxicity concerns or a subject may elect to stop study medication due to personal reasons. For temporary study drug discontinuations, study drug should be restarted after toxicity/safety concerns are resolved. In case of permanent study drug discontinuation, subjects should complete the visit associated with their current treatment cycle and then complete the EOS visit 4 weeks later (e.g. if a subject permanently stops study drug in the middle of their second treatment cycle, they will complete the end of treatment cycle visit 2 (C2) followed by an EOS visit 4 weeks later) (Figure 3). Subjects who do not agree to complete the 4 week post-treatment follow-up must be discontinued due to withdrawn consent and the Early Termination visit should be completed per Section 7.3.6 in place of the current treatment cycle visit.

	Cycle 1	Cycle 2	Cycle 3	Cycle 4	Cycle 5	Cycle 6	EOS	Comments
No Stopping	Green	Green	Green	Green	Green	Green	Green	
Stop during C1	Red	Grey	Grey	Grey	Grey	Grey	Green	Complete C1 and EOS visit 4 weeks later
Stop during C2	Green	Red	Grey	Grey	Grey	Grey	Green	Complete C2 and EOS visit 4 weeks later
Stop during C3	Green	Green	Red	Grey	Grey	Grey	Green	Complete C3 and EOS visit 4 weeks later
Stop during C4	Green	Green	Green	Red	Grey	Grey	Green	Complete C4 and EOS visit 4 weeks later
Stop during C5	Green	Green	Green	Green	Red	Grey	Green	Complete C5 and EOS visit 4 weeks later
Stop during C6	Green	Green	Green	Green	Green	Red	Green	Complete C6 and EOS visit 4 weeks later

**Figure 3. Follow-up visit schedule after permanent study drug discontinuation.** Dark Green: completed visits; Red: stop study medication mid-cycle.

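### Protocol Table 1B prints the platelet count for restarting study drug after a Grade 3 hold as >0.5 ×10⁹/L, a value below every Grade 3 count, so the printed number requires no recovery

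*Protocol*

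**What the plan says.** Protocol Section 6.1.8.3 handles haematologic toxicity through two tables. Table 1A gives the CTCAE grades, and its footnote sets one unit for all counts: "Units for blood cells counts are expressed as" 10⁹/L, equivalent to 10³ per microlitre. Platelets are Grade 2 at 50 to <75, Grade 3 at 25 to <50 and Grade 4 at <25.

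Table 1B gives the action for platelets at each grade:
- Grades 1 and 2: none.
- Grade 3: interrupt drug and check the CBC weekly. Then "Resume pomalidomide when platelets are $>0.5 \times 10^9/L", at a dose 1 mg/day lower.
- Grade 4: "Off study drug permanently".

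Two other places bear on restarting. Section 7.3.5 says: "For temporary study drug discontinuations, study drug should be restarted after toxicity/safety concerns are resolved". Section 6.1.8.4, on holds at the investigator's discretion, says: "Study drug can be resumed at the discretion of the investigator based on the investigator's opinion that it is safe to do so". Section 8.1 sends the management of thrombocytopenia back to Section 6.1.8. None of these gives a platelet count.

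**The concern.** Table 1B is where a site looks up the count at which a held patient may restart. A restart threshold has one job, which is to separate counts that have recovered from counts that have not. The printed value cannot do this, because it lies far below the range that triggered the hold and inside the range where the same row stops drug for good.

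It also sits badly with the stated intent of the section: "There is a lower threshold for intervention and/or discontinuation of pomalidomide for either neutropenia or thrombocytopenia than in multiple myeloma". That sentence concerns when to intervene or stop, not when to restart. Even so, a restart count of 500 platelets per microlitre is hard to reconcile with a scheme meant to be stricter than in myeloma.

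What is at stake is dosing safety. Participants have a bleeding disorder, entry required platelets of at least 100 ×10⁹/L (Section 5.1), and patients on stable anticoagulation or chronic aspirin are eligible (Section 7.5.1).

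**Working it through.** No sample-size, power or alpha figure is involved. The check compares the printed number with the grade limits in the same unit.

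**Size of the number.** By the Table 1A footnote, 1 ×10⁹/L = 1,000 per microlitre, so 0.5 ×10⁹/L = 500 per microlitre.
- Against the Grade 4 limit: 0.5 / 25 = 2%.
- Against the Grade 2/3 boundary: 0.5 / 50 = 1%. The boundary is 50 / 0.5 = 100 times the printed value.

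**Unit check.** The two units in the footnote are numerically the same, so neither rescues the value. For 0.5 to mean 50 ×10⁹/L, the unit would have to be 10¹¹/L, which the footnote does not list.

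**Restart rule against grade actions:**

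| Platelets, ×10⁹/L | Grade | Table 1B action | Meets >0.5? | Would meet >50? |
|---|---|---|---|---|
| 50 to <75 | 2 | none | yes | yes (except exactly 50) |
| 25 to <50 | 3 | interrupt | yes, every value | no |
| >0.5 to <25 | 4 | permanent stop | yes | no |
| 0.5 or less | 4 | permanent stop | no | no |

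Across the whole Grade 3 range, interrupting and resuming are both indicated at once. From >0.5 to <25, resuming and stopping permanently are both indicated. The resume instruction is free of contradiction only at 50 or above.

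**Parallel row.** For neutrophils the table says "Resume pomalidomide when ANC is $>1.0 \times 10^9/L". ANC Grade 3 is 0.5 to <1.0, so that restart count is the top of the Grade 3 range and no Grade 3 value meets it. The same construction for platelets gives >50. The parallel is not perfect: the Table 1B footnote sends one group, those kept on drug for up to a week at an ANC above 0.8 without recovering to 1.0, to a restart above 1.5.

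**Origin of the value.** The figure 0.5 is also the ANC Grade 3/4 limit. It could be a carry-over from the neutrophil scale, a slip for 50, or a digit misread from the PDF. The neighbouring neutrophil and platelet limits came through coherently, which makes a misread less likely but does not exclude it.

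**The case against.** The strongest reply is that the slip is evident and the tables correct it themselves. A site that resumed at 30 ×10⁹/L would at once be back in the Grade 3 cell, which says to interrupt. At 50 or above the table asks for nothing. So the grade structure already implies a boundary of at least 50. Section 7.3.5 separately requires the toxicity to have resolved. The medical monitor reviews all adverse events (Sections 10.4.7.1 and 15.1), and the DSMB reviews safety every six months (Section 8.6). This stands, and it limits the consequence considerably. It does not make the printed number right: a reader has to override one instruction in the cell with another to reach a sensible rule.

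A reader might infer more: that the protocol lets patients restart without recovering, that Grade 4 patients could be put back on drug, or that sites did restart at unsafe counts. The documents do not support these readings. Recovery is required in words, and Grade 4 is a permanent stop in the same row. Neither document reports how many Grade 3 platelet holds occurred or at what count anyone restarted.

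Two further points stand. The value 50 is inferred from the table's structure and stated nowhere, so the sponsor must confirm it. A site notice may also come late: the SAP reports both interim analyses as done (Section 9.6) and already contains blinded-review decisions on per-protocol exclusions (Section 5), site pooling (Section 7.6) and adverse event terms (Section 9.2). Dosing may be at or near its end.

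**Conclusion.** The platelet restart count is wrong as written, provided the source page reads as the extracted text does. It lies below 100% of Grade 3 counts and at 2% of the Grade 4 limit, and it is the only numeric platelet restart count in either document. These figures measure the size of the printed error, not the risk to patients.

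The practical effect is limited by the grade boundaries in the same tables, by Section 7.3.5 and by the medical monitor's review. Endpoints, alpha and power are untouched. The correction is worth making because it concerns a safety threshold and costs little.

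Two assumptions remain: that the digit was read correctly from the PDF, and that >50 ×10⁹/L is the intended value.

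**What to change.** 1. Check the cell on the source page. If it reads 50, nothing further is needed.
2. If it reads 0.5, the sponsor confirms the intended count, most likely >50 ×10⁹/L, and corrects the cell. If anyone is still on study drug, sites are notified.
3. If dosing has ended, limit the work to a record check of participants with any post-baseline platelet count below 50 ×10⁹/L, and list any restart made below 50. The SAP Section 9.2 category of <50 K/uL (the same unit) gives a first list, and thrombocytopenia adverse events of Grade 3 or above can supplement it. Match these to the dosing data behind SAP Section 8.3 and to the site medical record, which Protocol Section 11 names as the laboratory source. The site record is needed because Protocol Section 7.2.1.1 says "The Hgb, WBC, absolute neutrophil count (ANC) and platelet counts at all study visits will be recorded" and does not say that the weekly counts taken during a hold are entered.

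The cost is a one-cell correction, possibly a site memo, and a check confined to that subgroup. There is no statistical cost.

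Two matters are separate and not part of this correction. Table 1B does not say what follows a hold in a patient already at 2 mg/day, the lowest dose provided. The fixed 3 mg/day restarts for fatigue, liver and kidney toxicity (Sections 6.1.8.6, 6.1.8.10 and 6.1.8.11) do not address a patient already below 3 mg. Both are clinical rules for the sponsor to clarify.
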